9.3.1. Analysis Populations

The safety population will include all subjects enrolled in the study.

The outcome population will include all subjects in the study that received at least one dose of study medication and have at least one post-baseline measurement.

The study population will be compared to available normative data for age, as well as data from age-matched MPS I subjects not receiving IT rhIDU.

9.3.2. Study Conduct

Information about the study conduct will be summarized. Specifically details about the number of subjects completing or discontinuing the study will be summarized along with the reason for discontinuation. In addition, information about duration of enrollment and number of intrathecal doses will be summarized.

9.3.3. Safety analyses

Four categories of measurements related to safety will be examined:

9.3.3.1. Laboratory evaluations: CSF and anti-IDU antibody

Absolute, percent, and reference range change in CSF glucose, protein, and cell counts from the month 0 visit to the subsequent month visits will be calculated for each subject, and summarized over subjects with means, standard deviations, and 95% confidence intervals. Frequency and percent of subjects with values outside their reference range will be reported.

Absolute and percent change ELISA anti-IDU antibody from the month 0 visit to the subsequent month visits will be calculated for each subject, and summarized over subjects with means, standard deviations, and 95% confidence intervals. Frequency and percent of subjects with values outside their reference range for the subject's age will be calculated.

9.3.3.2. History and physical examination

At each visit, each subject will be classified as experiencing an adverse event if clinically significant worsening from baseline medical status, as described in Section 7.8.1.1, has occurred. The frequency and percent of subjects experiencing such an event will be tabulated for each visit.

9.3.3.3. Standard CBC and Chemistry Measurements

At each visit, each subject will be classified as experiencing an adverse event if there is clinically significant CBC or chemistry panel worsening from baseline, as described in Section 7.8.1.2.4. The frequency and percent of subjects experiencing such an event will be tabulated for each visit.

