The study will be conducted at the Los Angeles Biomedical Research Institute at Harbor-UCLA (LAB-HUCLA), Children's Hospital Oakland Research Institute

(CHORI) and the University of Minnesota (UMN). Additional study sites may be added as subjects are identified. Specific details are below:

- Recruitment: Subjects will be recruited from participants in the MIRC-002 study at LAB-HUCLA and CHORI.
- Procedures: Procedures will be performed at LAB-HUCLA, CHORI, and additional study sites that are added as subjects are recruited to the study. The addition of any new study site will be contingent upon approval by their local institutional review board (IRB), and the IRB at LAB-HUCLA. Neuropsychological testing will be performed at UMN.
- Regulations: The IRBs at CHORI and UMN will oversee the research at these respective sites, with LAB-HUCLA the primary site responsible.

4. Resources Available to Conduct the Human Research

Since subjects will be recruited from among participants enrolled in the pilot (MIRC-002) study:

- All participants are accessible for recruitment
- 67% are anticipated to be enrolled in the proposed study
- Study staff have previously been involved with participants and their families through the pilot study, so are familiar with local culture and attitudes toward clinical research.

Time requirement for the Principal Investigator to conduct and complete the proposed study within the agreed trial period is projected to be 8 hours per week.

Site study staff at the LAB-HUCLA include six members: two co-Primary Investigators, two pharmacists, one Study Coordinator, and one laboratory staff. Study staff at the CHORI site include three members: one site PI, one pharmacist and one study coordinator. Study staff at the UMN include two members: one site PI and one study coordinator. All study staff have completed appropriate training regarding protection of human research subjects, Good Clinical Practices, and HIPAA, and have previously participated in other clinical research trials.

Inpatient study treatments are conducted at the hospital in an area designated for clinical research and study evaluations are completed in separate outpatient clinical research facilities. Principal Investigators have hospital privileges at their respective sites and non-study staff resources are available at each hospital should study participants require medical or psychological support as a result of an anticipated consequence of the research study.

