6.4. Study Timelines

The duration of each subject's participation in the study is expected to be five years. We anticipate enrolling these subjects over a 4-year period. The estimated date of completion of the study is 10 years following the onset of the study.

7. Procedures Involved in the Human Research

This study is a five-year open-label, prospective trial in 6 MPS I subjects age six years or greater who have completed a 24-month open label study (MIRC-002). Potentially eligible subjects who (or, if appropriate whose parents or guardians) have provided signed, written informed consent will first participate in a baseline screening phase. This will occur at least six months after subjects have completed the MIRC002 pilot study. During baseline screening, the subjects will receive the baseline evaluations outlined below, and their eligibility will be determined. Every three months, subjects will receive intrathecal recombinant human α-L-iduronidase (IT rhIDU) approved as Aldurazyme® [laronidase] for the treatment of cognitive impairment in patients with mucopolysaccharidosis I (MPS I). Neuropsychological testing and MRI will be performed at baseline and at one year intervals. Safety will be monitored continuously throughout the subject's study participation through recording all adverse events (AEs) and periodically performing clinical and laboratory evaluations.

Study subjects will receive intrathecal enzyme therapy only during the study; intrathecal enzyme therapy will not be administered at the end of the five-year period. If further intrathecal enzyme is desired, the subject may enroll in further intrathecal research if another study is available.

To assure that subjects enrolling in the trial have maximum access to alternative therapy, subjects will be asked to receive counseling regarding other available appropriate medical and surgical alternatives prior to enrollment in this trial.

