7.2. Schedule of Study Evaluations

After obtaining informed consent, the investigator will conduct the study as outlined in the following sections. Table 1 summarizes the nature of the assessments and treatments and their timelines. Refer to Study Operations Manual for guidelines regarding test assessments and procedures for handling/shipment of all central laboratory samples.

Table 1 Schedule of study assessments and treatments

Month Number	Baseline	Visit 1/Odd Numbered Visits	Visit 2/Even Numbered Visits	End Study
Neuropsychological testing	X		yearly	
MRI of brain	X		yearly	
Clinical tests				
History and Physical examination	X	X	X	X
Neurologic examination	X	X	X	X
Photography and video (optional)	X	X	X	X
Six-minute walk test	X	X	X	X
Subjective response of clinical symptoms	X	X	X	X
FIM scoring	X	X	X	X

Laboratory tests (CSF)				
Protein, glucose, cell count		X	X	
GAG levels		X	X	
Anti-rhIDU antibody		X	X	
CSF iduronidase assay		X	X	
Laboratory tests (blood)				
Anti-rhIDU antibody	X	X	X	X
CBC, Chem panel 20, Coagulation studies	X	X	X	X
Neurophysiologic test				
CSF flow study	X			
Investigator Global Assessment				
	X	X	X	X
Treatments				
Intrathecal rhIDU		X	X	

Visits occur at three-month intervals starting from Visit One. There may be a variable period between Baseline/Screening and Visit One from five days to three months. If the period between Baseline/Screening and Visit One is less than one week, then all of the other assessments do not need to be repeated for Visit One.

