7.8.1.2. Laboratory Evaluations

7.8.1.2.1. CSF chemistry and cell counts

Glucose, protein, and cell counts will be recorded in their standard units. The subject's levels will be compared to age-matched normative controls from that laboratory. Data will be kept as quantitative, continuous variables, and each subject assessed for change over the study period.

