9.2. Study Size

A study size analysis was done for the pilot study. As this study is only open to subjects that have completed the pilot study, the maximum number of subjects available for this study is six.

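### Section 9.3.3.3 reduces serial CBC and chemistry values to a per-visit count of one pooled flag, and coagulation has no analysis of its own, so a shared drift below the flag's threshold would not show in the planned tables

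*Combined protocol and SAP*

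**What the plan says.** Table 1 in Section 7.2 schedules CBC, a chemistry panel and coagulation tests at baseline, at odd and even visits and at end of study. "Visits occur at three-month intervals starting from Visit One", and Section 6.4 sets five years per subject. One small exception is that assessments need not be repeated at Visit One if baseline was less than a week earlier.

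For CBC and chemistry, Section 9.3.3.3 states that "each subject will be classified as experiencing an adverse event if there is clinically significant CBC or chemistry panel worsening from baseline". The only summary is this: "The frequency and percent of subjects experiencing such an event will be tabulated for each visit". The section takes its definition from Section 7.8.1.2.4, which does not exist. The definition is in Section 7.8.1.2.2, where the investigator rates each abnormal value as clinically significant or not, and worsening must lead to a change in care.

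CSF safety laboratory values are treated differently. Section 7.8.1.2.1 says: "Data will be kept as quantitative, continuous variables, and each subject assessed for change over the study period". Section 9.3.3.1 has their absolute and percent changes "summarized over subjects with means, standard deviations, and 95% confidence intervals. Frequency and percent of subjects with values outside their reference range will be reported".

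Coagulation has no subsection in 9.3.3. A clotting abnormality judged clinically significant is an adverse event under Section 12.1 and would be counted under Section 9.3.3.4.

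Section 9.1 gives the statistical goal as estimating the size and heterogeneity of changes, as well as calculating adverse event rates. On size, Section 9.2 says "the maximum number of subjects available for this study is six", and Section 4 says "67% are anticipated to be enrolled in the proposed study".

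**The concern.** Long-term safety is the first objective, and the study collects about 20 serial values per analyte per subject towards it. The planned table keeps one yes/no answer per subject per visit. That answer pools the whole panel, so the count does not show which analyte moved, in which direction or by how much.

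If an analyte moves moderately in every subject but nobody's care changes, the table reads zero at every visit. The plan would then have the numbers to describe the shift but no output that does so. This includes platelets and clotting times, which Section 6 treats as important enough to carry numeric exclusion limits in a study of repeated lumbar puncture.

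**Working it through.** The plan gives no power, effect size or SD for laboratory change, so there is no figure of its own to reproduce.

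**Inputs from the documents.**
- Maximum n = 6 (Section 9.2).
- Anticipated uptake of 67% (Section 4): 0.67 × 6 = 4.02, about 4 subjects.
- Five years at three-month intervals: 60 / 3 = about 20 visits.
- 95% intervals, as in Section 9.3.3.1.

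**1. What a zero count can exclude.** The exact two-sided 95% upper limit for 0/n is 1 − 0.025^(1/n).
- n = 6: 1 − 0.025^(1/6) = 0.459, or 46%.
- n = 4: 1 − 0.025^(1/4) = 0.602, or 60%.

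**2. How often a shared drift leaves the count at zero.** This part rests on assumptions that are not in the documents: normally distributed values, an upper reference limit at +1.96 SD, independent subjects, one analyte, one visit, and a fraction q of out-of-range values judged clinically significant. A drift of d reference SDs puts p = 1 − Φ(1.96 − d) of values out of range, and P(no flag) = (1 − pq)^n.

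| Drift d | p | n = 6, q = 0.5 | n = 6, q = 0.25 | n = 4, q = 0.5 | n = 4, q = 0.25 |
|---|---|---|---|---|---|
| 0.5 SD | 0.072 | 80% | 90% | 86% | 93% |
| 1 SD | 0.169 | 59% | 77% | 70% | 84% |
| 2 SD | 0.516 | 17% | 44% | 30% | 58% |

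For example, with d = 1, q = 0.5 and n = 6: (1 − 0.169 × 0.5)^6 = 0.59. With d = 2, at least one of six is out of range with probability 1 − (1 − 0.516)^6 = 0.987. A large drift would therefore produce abnormal values, but a table of events would still not show it as a common shift.

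**3. What the Section 9.3.3.1 summary would give instead.** The 95% interval for a mean change has half-width t(0.975, n − 1)/√n, in SDs of change.
- n = 6: 2.571/2.449 = 1.05 SD.
- n = 4: 3.182/2 = 1.59 SD.

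These intervals are wide. They show direction and plausible size, and they do not support a firm conclusion on any one analyte.

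**4. Does the continuous summary detect drift better?** Not in general. A simulation compared a paired t interval lying above zero with at least one subject newly above the upper limit. It used a single follow-up visit and a within-subject SD of w population SDs.

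| n | w | Shift | t interval above zero | At least one newly out of range |
|---|---|---|---|---|
| 6 | 0.3 | 0.75 SD | 93% | 43% |
| 6 | 0.7 | 1.0 SD | 51% | 63% |
| 4 | 0.5 | 0.75 SD | 32% | 33% |

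In the second and third rows the out-of-range rule also fires more often when there is no shift: about 12% and 6%, against 2.5% for the t interval. In the first row's setting, counting a subject out of range at any of 20 visits raises 43% to about 79%, and to about a quarter with no drift at all. The comparison is driven by the assumptions, so the point does not rest on it.

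**The case against.** The strongest reply is that this is a choice and not an oversight. Treatment is intrathecal, so CSF values and antibodies get quantitative summaries while routine bloods get event counts. Section 7.8.1.2.2 also notes that values may be abnormal because of the underlying disease, which is why judgment is asked for. That explains having a flag. It does not explain discarding the numbers, given the estimation goal in Section 9.1.

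A reader might infer that a drift would go entirely unseen. The documents do not support that. The investigator rates every abnormal value, Section 12.6 gives the DSMB interim and cumulative data, Section 12.7 has it meet every four months with a statistician among its members, and Section 8 keeps the data. What is missing is a planned output, and the protocol does not say what the DSMB reports contain.

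A reader might also infer that clotting results are ignored. They are not: clinically significant abnormalities reach the adverse event table. Their course over time has no summary.

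A third tempting reading is that a continuous analysis is clearly more powerful. The simulation shows this only for stable analytes in six subjects, under variances the documents do not supply.

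Two practical objections stand. Section 7.7.4.2 names 16 chemistries and three coagulation tests, so 19 × 20 = 380 mean changes before any CBC component is added. In addition, subjects may enter at age six, are followed for five years without a concurrent control, may receive intravenous enzyme, and are tested in local laboratories. A mean change would mix all of these with any drug effect.

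**Conclusion.** The point holds as a gap in the planned reporting. Section 9.3.3.3 applies a coarser method to serial numeric data than the plan applies to CSF values, and coagulation has no analysis beyond adverse event tabulation. In four to six subjects a shared drift below the altered-care threshold would not appear in the planned tables.

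The upper limits of 46% for 0/6 and 60% for 0/4 follow from the sample size alone. The no-flag probabilities in step 2 rest on assumed drifts, normality and a guessed share of values judged significant, and serve only as illustration. Nothing here shows that a harmful change would be missed clinically, or that an added interval would reliably detect one. It is worth correcting because the values are already collected and the plan already contains the method.

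**What to change.** In Section 9.3.3.3:

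- Keep the adverse event flag and its per-visit count.
- For CBC, chemistry and coagulation, add the Section 9.3.3.1 summary: absolute change from baseline by visit with mean, SD and 95% confidence interval, and the number and percent outside the age-appropriate local reference range.
- Add individual subject profiles over all visits for key analytes such as platelets, INR/PTT, AST, ALT and creatinine.
- Label the intervals descriptive and unadjusted for the number of analytes and visits. Add no significance test and no slope model.
- State that growth, underlying disease, intravenous enzyme therapy and differences between local laboratories may contribute to any change in this uncontrolled study.
- Retitle the section to include coagulation, and correct the reference from Section 7.8.1.2.4 to Section 7.8.1.2.2.

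The cost is analysis-plan wording and a sizeable set of extra tables and plots, with many wide intervals that need cautious reading. No new visits, samples or tests are required.

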9.3.3.4. Other Adverse Events

Other adverse events and unexpected adverse events from the time of injection to the time of subsequent injection will be recorded for each subject. The frequency and percent of subjects experiencing any such event will be tabulated for each post-injection interval, and for the entire month 0 to end study interval.

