7.7.5. Neurophysiologic evaluation

7.7.5.1. CSF flow study

At baseline screening, the subject will undergo a CSF flow study. This study is performed by injecting radionuclide (e.g. 99m Technetium-DTPA) into the lumbar cistern. Access to the lumbar cistern may require fluoroscopic-guided assistance due to body habitus or disease-related changes to the lumbar bony and ligamentous structures. Images will be obtained using a scintillation camera as the radionuclide flows caudally. Time to appearance of the radionuclide to specific CSF compartments will be compared to established norms (Chamberlain 1998). This study will guide our decision as to whether a lumbar approach for the intrathecal injection can be performed.

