12.1. Adverse Events

Subjects in this study will be closely monitored during the enzyme administration and for one hour afterward with frequent (every 15 minutes) vital signs and continuous pulse oximetry. The subject will be able to contact the investigator or other appropriate personnel to report adverse events occurring later. These will be treated with appropriate medical care where applicable. Adverse events that are unanticipated will be reported within 10 working days to the institutional review board.

An adverse event (AE) is any undesirable physical, psychological or behavioral effect (an unfavorable and unintended sign, symptom or disease) experienced by a subject during their participation in an investigational study whether or not product-related. This includes any untoward signs or symptoms experienced by the subject from the time of signing of the informed consent until completion of the study. Adverse events may include, but are not limited to:

- Subjective or objective symptoms spontaneously offered by the patient or subject and/or observed by the investigator or medical staff.
- Laboratory abnormalities of clinical significance.
- Disease signs, symptoms and/or laboratory abnormalities already existing prior to the use of the study medication are not considered adverse events after treatment unless they reoccur after the subject has recovered from the pre-existing condition or they represent an exacerbation in intensity or frequency.

All reportable AEs will be assigned a relationship to the study drug by the principal investigator. A drug-related AE is an event with a plausible time relationship to drug intake that cannot be explained by the disease or other drugs.

Any AEs experienced by the subject, from the time of signing the Informed Consent Form through the completion of study participation, will be reported as described (see Section 11.3) and recorded on the CRF. If AEs are present when the patient completes study participation, the subject will be re-evaluated within two weeks of completion and the results of this re-evaluation will be recorded on the CRF. If AEs are not resolved, additional follow-up will be performed as appropriate. All reportable AEs must be reported to the RDCRN within **20 working days** of the notification of the event or of the site becoming aware of the event.

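### The catch-all adverse event table (Section 9.3.3.4) has no row for the time between consent and the first rhIDU injection, and month 0 is not defined

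*Combined protocol and SAP*

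**What the plan says.** All references are to the combined protocol and SAP.

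- **Collection (12.1).** The reporting window covers "Any AEs experienced by the subject, from the time of signing the Informed Consent Form through the completion of study participation".
- **Catch-all table (9.3.3.4).** "Other adverse events and unexpected adverse events from the time of injection to the time of subsequent injection will be recorded for each subject". The next sentence says that the frequency and percent of subjects with such events will be shown by post-injection interval and "for the entire month 0 to end study interval".
- **Baseline procedure (7.7.5.1).** "At baseline screening, the subject will undergo a CSF flow study. This study is performed by injecting radionuclide" into the lumbar cistern, with fluoroscopic guidance if needed. Section 15.5 confirms that this is a spinal tap and lists back pain, headache and, rarely, spinal headache among its risks.
- **Timing (7.2).** "There may be a variable period between Baseline/Screening and Visit One from five days to three months". If the gap is under one week, the other assessments need not be repeated at Visit One.
- **Other adverse event tables.** Sections 9.3.3.2 (history and physical examination) and 9.3.3.3 (CBC and chemistry) classify each subject at each visit by clinically significant worsening from baseline.
- **Population (9.3.1).** The safety population is everyone enrolled. Under 7.3, subjects who do not meet the criteria are not enrolled.

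**The concern.** The collection window and the tabulation window do not match. Collection starts at consent. The only table meant to catch events of any kind starts, by its own wording, at an injection of study drug. In between lies an invasive procedure required by the protocol, with stated risks.

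Long-term safety is the first objective in Section 1, and Section 9.1 names the calculation of adverse event rates as part of the statistical goal. If the final analysis follows 9.3.3.4 literally, a post-puncture headache that resolves before Visit One is recorded on the case report form but has no place in the main adverse event summary. With so few subjects, a single such event is visible in any percentage.

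**Working it through.** The plan gives no figure for this gap, so there is none to reproduce. The check has two parts: what each table covers, and how large the uncovered part is.

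**Step 1: does the meaning of month 0 close the gap?** Table 1 has no month 0 column, and the analysis sections use the term in two senses.

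- In 9.3.3.1, change in CSF chemistry runs from month 0. Table 1 has no CSF chemistry at baseline, so month 0 there must be Visit One.
- In 9.3.4.2.2, change in MRI runs from month 0. MRI is done at baseline and yearly, so month 0 there must be baseline.

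If month 0 in 9.3.3.4 is Visit One, the overall row starts after the flow study. If it is baseline, the row starts early enough, but the events it counts are still those defined in the preceding sentence, that is, events between injections. Section 9.1 uses injections to mean rhIDU. Either way, no row for the time before the first dose is named.

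**Step 2: do the other two Section 9 tables cover it?** Partly.

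- The table in 9.3.3.2 can count an event as worsening from baseline at Visit One. By the definition in 7.8.1.1, it must have led to a change in medical care. A headache that resolved without such a change would not qualify, and with a gap under one week the Visit One examination may not be repeated.
- The table in 9.3.3.3 covers only blood counts and chemistry.

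**Step 3: size of the gap.** Inputs: dosing every three months for five years (Section 7), at most six subjects (9.2), and a gap of 5 days to 3 months (7.2). No dose count is stated, so 20 is an assumption (5 × 4), with 21 as a check.

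| Quantity | Calculation | Result |
|---|---|---|
| Punctures per subject, 20 doses | 20 + 1 | 21 |
| Share in the gap, 20 doses | 1/21 = 6/126 | 4.8% |
| Share in the gap, 21 doses | 1/22 = 6/132 | 4.5% |
| Radionuclide injections in the gap | 1 of 1 per subject | all |
| Shortest gap as share of five years | 5 / (5 × 365.25) | 0.3% |
| Longest gap as share of five years | (3 × 30.4375) / (5 × 365.25) | 5.0% |
| Person-days, six subjects | 6 × 5 to 6 × 91.3 | 30 to 548 |
| One affected subject of six | 1/6 | 16.7 percentage points |

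The last line applies to a consent-to-end percentage only if that subject has no later event.

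**Step 4: is an event in the gap likely?** The documents give no event rate after a puncture. For an assumed per-subject probability p, the chance of at least one affected subject among six is 1 − (1 − p)^6.

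| Assumed p | Expected subjects (6p) | Chance of at least one |
|---|---|---|
| 5% | 0.3 | 27% |
| 10% | 0.6 | 47% |
| 20% | 1.2 | 74% |
| 30% | 1.8 | 88% |
| 40% | 2.4 | 95% |

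**Step 5: who stays outside even with a new row?** Exclusion criterion 7 (impaired CSF flow) is judged from the flow study itself. A subject can therefore have the puncture, fail screening, not be enrolled and fall outside the safety population.

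**The case against.** The strongest reply is that these events are not lost. Serious events are reported within 24 hours (12.3). The periodic report lists all adverse events with severity and attribution (12.7). The DSMB receives tables of non-serious expected events, and the data centre posts aggregate reports of all adverse events (12.8). The two per-visit tables are not tied to month 0, and an interim history is taken at each later visit (7.7.3.1). A reader might infer that events after the baseline procedure appear in no safety table, or that every adverse event table starts at month 0. The documents support neither reading: only one of the three Section 9 adverse event tables has that window, and the monitoring reports have no such limit.

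It can also be said that tabulating by post-injection interval suits the objective, which is the safety of intrathecal rhIDU, and that the uncovered time may be only five days. Both are fair and keep the point minor.

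What does not stand is that this coverage replaces the missing row. Monitoring reports protect subjects during the trial, but they are not the planned analysis with frequencies and percents. The per-visit tables catch such an event only under the conditions in Step 2. Counting the radionuclide as the first injection would close the gap, but nothing in Section 9 suggests that meaning.

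**Conclusion.** The point holds in a narrow form. The table in 9.3.3.4 has no interval before the first dose under either reading of month 0, and month 0 itself is undefined. A transient event after the baseline puncture and radionuclide has no row there. It may appear in a per-visit table if it counts as worsening, and otherwise only in monitoring reports.

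The gap is about 5% of lumbar punctures (assuming 20 doses), all radionuclide injections, and 0.3% to 5% of a five-year follow-up. It does not affect the primary outcome or subject protection during the trial. It is a minor improvement to reporting.

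A reader might also infer that a row for this period would give a drug-free comparison for the post-dose intervals. It would not: the procedure injects a radionuclide, happens once per subject in at most six subjects, and follows earlier treatment in MIRC-002. No such comparison is planned.

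**What to change.** In Section 9.3.3.4:

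1. Define month 0 as the first rhIDU injection of this study.
2. Add a separate row for events from consent to first injection.
3. Keep the total from first injection to end of study as its own line. If a total from consent is also wanted, show it separately; merging the two would mix events before and after dosing in one percentage.
4. List separately the adverse events of subjects who had the flow study but were not enrolled, since a row based on the safety population cannot include them.

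The cost is one definition, one or two table rows and a short listing. Section 12.1 already requires collection from consent, so no new data, visits or procedures are needed.
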